#### **8.3.2. DSP-7888 Dosing Emulsion Dose Modification in Phase 2**

Both dose interruption and dose reductions are allowable for DSP-7888 Dosing Emulsion.

##### **8.3.2.1. Dose Reduction**

After the induction phase, dose reduction to 3.5 mg and subsequently to 1.75 mg is permitted due to ISR if the investigator considers that a dose reduction is medically required. No further dose reductions from 1.75 mg will be allowed. Re-escalation of the dose after dose reduction is not permitted.

##### **8.3.2.2. Dose Interruption**

DSP-7888 Dosing Emulsion must be interrupted for any CTCAE (v.4.03) Grade 3 or 4 AE that the investigator considers to be related to DSP-7888 Dosing Emulsion. If toxicity is resolved to Grade 1 or less/baseline, the patient may restart treatment with DSP-7888 Dosing Emulsion but with a dose level reduction.

EXCEPTION: Because more serious ISRs (eg, Grade 3) may take longer to resolve due to the tissue injury, resolution to Grade 2 only is required for restart of treatment with DSP-7888 Dosing Emulsion. However, no dose reduction is required for following cases:

- Grade 3 or 4 hematologic laboratory abnormality which resolves to Grade 1 or less within 7 days without supportive care (blood transfusion or G-CSF agents)
- Grade 3 or 4 non-hematologic laboratory abnormality which resolves to Grade 1 or less within 7 days
- Grade 3 ISR that does not require hospitalization; patients may continue on the study treatment per investigator's judgment
- Grade 3 fatigue, fever, malaise, edema per CTCAE (v.4.03), which resolves to Grade 1 or less within 5 days, with appropriate supportive care
- Grade 3 nausea, vomiting, diarrhea per CTCAE (v.4.03), which resolves within 3 days, with appropriate supportive care

Before discontinuation of dosing for any of the above reasons, a conversation with the Medical Monitor may be applicable.

If toxicity is not resolved to Grade 1 or less (or Grade 2 or less in the case of ISRs, as described above) within 4 consecutive missing doses and, in the opinion of the investigator, the patient is clinically stable and receiving benefit from study drug, the patient may restart treatment with DSP-7888 Dosing Emulsion at a reduced dose on a case-by-case basis, only after consultation with the Sponsor.

### **8.3.3. Pembrolizumab and Nivolumab Dosing Management in Phase 1b and Phase 2**

The product labels/package inserts (refer to pembrolizumab and nivolumab), have identified several immune system toxicities as related to the use of pembrolizumab and nivolumab. Dose management (dose withholding or permanent discontinuation) should be performed based on the recommendations in the respective product label.

### **8.3.4. Settings and Recommendations for DSP-7888 Dosing Emulsion Injections**

Whenever possible, injections should be administered into the area surrounding the regional lymph nodes in the upper arm, the lower abdomen, or the femoral area.

To the extent possible, injections of study drug should be administered to separate parts of the body and separated from one another. Rotation of injection sites is recommended. Injection sites should not be chosen in the area of any ongoing skin condition (eg, an area of psoriasis).

### **8.3.5. Evaluation and Management of Injection Site Reactions**

#### **8.3.5.1. Evaluation of Injection Site Reactions**

The type of ISR should be reported for the AE verbatim term (eg injection site redness should be reported as injection site redness, and not injection site reaction). Injection site reactions will be graded according to CTCAE v4.03 ([Table 11](#)).

**Table 11: Grading of Injection Site Reactions (CTCAE v4.03)**

Grade 1	Grade 2	Grade 3	Grade 4
Tenderness with or without associated symptoms (eg, warmth, erythema, itching)	Pain; lipodystrophy; edema; phlebitis	Ulceration or necrosis; severe tissue damage; operative intervention indicated	Life-threatening consequences; urgent intervention indicated

Factors other than the appearance of the ISR should be taken into consideration when evaluating the severity of an ISR. A pinpoint ulcer, for example, truly may not be indicative of a Grade 3 ISR; other factors, such as the presence of fever or the need for systemic analgesia, also should be considered in determining ISR severity, and in guiding decisions regarding temporary discontinuation and/or dose reductions of DSP-7888 Dosing Emulsion.

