1.1. Study Design

This is a Phase 1b/2, open-label, multicenter study of DSP-7888 Dosing Emulsion in combination with checkpoint inhibitors (nivolumab or pembrolizumab) in adult patients with solid tumors, that consists of 2 parts: Phase 1b (a dose search part and an enrichment part) and Phase 2 dose-expansion. In the Phase 1b part of this study there will be 2 arms: Arm 1 and Arm 2. In Arm 1, there will be 6 to 12 patients who will be dosed with DSP-7888 Dosing Emulsion and nivolumab and, in Arm 2, there will be 6 to 12 patients who will be dosed with DSP-7888 Dosing Emulsion and pembrolizumab.

In addition, a Phase 1b enrichment cohort of a further 10 patients, who have locally advanced or metastatic renal cell carcinoma (RCC) or urothelial cancer with primary or acquired resistance to previously administered checkpoint inhibitors, will be enrolled and will be dosed with DSP-7888 Dosing Emulsion and nivolumab, or DSP-7888 Dosing Emulsion and pembrolizumab, as per the investigator’s preference. The purpose of this Phase 1b enrichment cohort is to help evaluate the preliminary antitumor activity of DSP-7888 Dosing Emulsion at the safe dose level identified in the Phase 1b dose-search part.

Once the recommended dose is determined in the Phase 1b dose search part, platinum-resistant ovarian cancer (PROC) patients will be enrolled in the Phase 2 part of the study and treated with DSP-7888 Dosing Emulsion, exploring the combination with pembrolizumab. In Phase 2, a total of approximately 40 patients with PROC will be enrolled. Additional patients may be enrolled to further assess anti-tumor activity in the subgroups of interest. However, the total sample size of Phase 2 part cannot exceed 60 patients.

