5.4.1. Adverse Events

Treatment-Emergent Adverse Events

An AE will be regarded as treatment-emergent, if

- it occurs for the first time on or after the first dose date of either DSP-7888 or CPI up to 30 days after the last dose of study drug; or
- it occurs up to any time if serious and considered related to study drug.

The emphasis for AE analysis will be based on treatment-emergent AE (TEAE), however all AEs will be listed.

All AEs will be coded using Medical Dictionary for Regulatory Activities (MedDRA version 20.0) and summarized by MedDRA System Organ Class and Preferred Term. The severity of all AEs will be graded by the Investigator using NCI CTCAE version 4.0.

An overview of treatment-emergent adverse events (TEAEs) will be provided. The number and percentage of subjects with following will be summarized for phase 1b, Arm 1 and Arm2 overall, phase 2: CPS < 10, CPS \geq 10 and Overall.

- Subjects with any TEAE
- Subjects with TEAE of CTCAE grade 3 or higher
- Subjects with serious adverse events (all causality and related)
- TEAEs related to study drug
- TEAEs related to study drug with CTCAE grade 3 or higher
- Subjects with TEAE leading to study drug discontinuation (all causality and related)
- Subjects with TEAE leading to study drug dose reduction (all causality and related)
- Subjects with TEAE leading to study drug dose interruption (all causality and related)

Summary of AEs by SOC and Preferred Term

The number and percentage of subjects with TEAEs by SOC, PT and maximum CTCAE grade will be summarized. A summary of TEAEs of CTCAE grade 3 or higher (Grade 3, 4, 5) will be presented by SOC and PT and maximum CTCAE grade (All Grade, \geq Grade 3).

The number and percentage of patients who experience any TEAE will be summarized by SOC and PT (All Grade, \geq Grade 3). A summary of TEAEs by PT and maximum CTCAE grade will be presented. The most commonly reported TEAEs using a different cutoff (e.g. 2% or 10% or more of patients in either arm) may also be summarized by PT as needed.

TEAEs associated with permanent discontinuation /dose reduction/drug interruption of either DSP7888 and/or CPI will be summarized by SOC and PT and maximum CTCAE Grade (taking into consideration the action taken from CRF AE page).

Treatment Related Adverse Events

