Treatment-related TEAEs are those judged by the investigator to be at least possibly related to the study drugs (DSP7888 and/or CPI) or for which relatedness is recorded as “unknown” by the investigator. Treatment related will include “possible”, “probable” or “definite” causality assessments. Missing relationship will be considered as “Related” to all drugs received by the patient. Similar summaries as noted for all causality TEAEs will be provided for treatment related TEAEs.

Serious Adverse Events and Death

Treatment-emergent SAEs and Treatment-related SAEs will be summarized by MedDRA SOC and PT and maximum CTCAE grade.

TEAE leading to death will be summarized by MedDRA SOC and Preferred Term.

Deaths will be summarized by on study and on treatment (within 30 days of last dose of study medication). The number and percentage of patients who died on study and on treatment, as well as primary cause of death will be summarized. Deaths may also be categorized according to time of occurrence after first dose.

A listing of death data will also be provided and will include all deaths that occurred from the signing of the informed consent to the end of the follow up period. The listing will include primary cause of death and the number of days relative to the administration of first and last dose.

Adverse Events of COVID-19

Preferred Terms corona virus infection and coronavirus test positive will be used to identified COVID-19 positive cases in adverse event.

Injection Site Reaction (ISR)

The predominant adverse effect observed with DSP-7888 is injection site reaction. The Preferred Terms of TEAEs within the High Level Group Term of “Administration Site Reaction” (MedDRA version 20.0) will be used to identify events of injection site reaction.

Below analysis will be provided for ISR:

- ISR by SOC, PT, and maximum CTCAE Grade
- Onset time of first ISR for patients with at least one ISR: Time to onset is analyzed for patients with at least one ISR from the first dose of the DSP-7888 to the first occurrence of ISR regardless of CTCAE grade.
- Onset time of first ISR: Time to first ISR is defined as the time from the first dose of the DSP-7888 to the first occurrence of ISR . For patients with no ISR, the onset time will be censored as data cutoff date,

end of study date, death date, or safety follow-up completion date (end of treatment date + 30 days) whichever is shorter.

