- Onset time of the first Grade 3 or higher ISR for patients with at least one Grade 3 or higher ISR: Time to onset is analyzed for patients with at least one Grade 3 or higher ISR from the first dose of DSP-7888 to the first occurrence of the Grade 3 or higher ISR.
- Onset time of the first Grade 3 or higher ISR: Time to first Grade 3 or higher ISR is defined as the time from the first dose of DSP-7888 to the first occurrence of the Grade 3 or higher ISR. For patients with no Grade 3 or higher ISR, the onset time will be censored as data cutoff date, end of study date, death date, or safety follow-up completion date (end of treatment date + 30 days) whichever is shorter.
- Duration of ISR and Duration of Grade 3 or higher ISR and may be analyzed in the CSR. The duration is defined as (end date – start date + 1), and for ongoing ISR/ or ongoing Grade 3 or higher ISR, the ISR end date is truncated as the minimum of {by data cutoff date, end of study date, death date, last known to be alive date, or safety follow-up completion date (end of treatment date + 30 days)} whichever is shorter.

A listing of ISR will also be provided.

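### Table 11 puts injection-site ulceration in Grade 3, but the paragraph below it lets a pinpoint ulcer be graded lower, so Grade ≥3 injection site reaction counts and onset times can depart from the CTCAE scale they cite

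*Protocol*

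**What the plan says.** Protocol 8.3.5.1 fixes the scale: "Injection site reactions will be graded according to CTCAE v4.03". Table 11 reproduces that scale, and its Grade 3 cell reads "Ulceration or necrosis; severe tissue damage; operative intervention indicated". The cell carries no size or symptom qualifier for an ulcer.

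The paragraph directly below the table says "A pinpoint ulcer, for example, truly may not be indicative of a Grade 3 ISR". It goes on: "other factors, such as the presence of fever or the need for systemic analgesia, also should be considered in determining ISR severity". The same sentence mentions decisions on stopping or reducing the vaccine as a further use of these factors.

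On the analysis side, SAP 5.4.1 states "The severity of all AEs will be graded by the Investigator using NCI CTCAE version 4.0". Its planned ISR outputs include "ISR by SOC, PT, and maximum CTCAE Grade" and an onset analysis: "Time to first Grade 3 or higher ISR is defined as the time from the first dose of DSP-7888". It also plans tables of Grade 3 or higher treatment-emergent events, and it may report the duration of Grade 3 or higher ISRs.

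Protocol 8.3.5.1 also asks sites to name the type of reaction in the verbatim term rather than write a generic ISR term.

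**The concern.** A recorded grade is comparable between patients, sites and studies only if everyone applies the same rule. Here one subsection holds two rules for the same lesion. On Table 11 a pinpoint ulcer is Grade 3. On the paragraph below it, the ulcer may be something less. Pinpoint is not defined, no weight is given to fever or analgesia, and no replacement grade is named. Investigators do the grading in a multicenter study, and neither document describes adjudication of ISR grade.

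ISRs are central to this safety profile. SAP 5.4.1 calls them the predominant adverse effect, the severity of adverse events is part of a Phase 1b primary endpoint, and SAP Section 5 limits the final report to safety. Outputs labelled as CTCAE grades would be read, and compared with other CTCAE-graded studies, as if Table 11 had been applied as written. Nothing in the SAP tells the reader otherwise.

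**Working it through.** The plan gives no expected Grade ≥3 ISR rate, share of pinpoint ulcers or grading-agreement figure, so there is no figure to reproduce. The check is a comparison of texts followed by an illustration on assumed inputs.

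**Does the paragraph change the grade, or only management?** It changes the grade. The sentence on other factors names severity and dosing decisions as two separate things to be informed, and the pinpoint-ulcer clause is about the grade itself.

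**Which way can the grade move?**

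- For an ulcer that meets the Table 11 Grade 3 entry, the named example points only downward.
- For other reactions, fever or systemic analgesia could raise a Grade 1 or 2 reaction. The text sets no direction and no threshold.

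**Which outputs move with it?** Take a patient whose only Grade 3 feature is a regraded ulcer.

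- The patient leaves the Grade ≥3 event tables and appears at a lower maximum grade in the ISR table.
- In the time-to-first-Grade ≥3 analysis the patient is censored, or is counted later if a further Grade ≥3 reaction follows.
- The time to first ISR of any grade does not change.

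**Illustration.** Let p be the share of patients at Grade ≥3 when Table 11 is read literally. Let f be the share of those patients regraded below 3. Both are assumptions. Patients who qualify through necrosis, severe tissue damage, operative intervention or Grade 4 are not named in the paragraph, so they would keep f below 1.

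Reported rate = p × (1 − f). For N = 40, the planned Phase 2 size:

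| p | Table 11 count | f = 0 | f = 10% | f = 25% | f = 50% |
|---|---|---|---|---|---|
| 10% | 4 | 4 | 3.6 | 3 | 2 |
| 20% | 8 | 8 | 7.2 | 6 | 4 |
| 30% | 12 | 12 | 10.8 | 9 | 6 |

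Phase 2 ended on interim monitoring, which could start after 20 patients, so the actual N may be smaller. At N = 20 and p = 20%, a Table 11 count of 4 is reported as 4 (f = 0) down to 2 (f = 50%).

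Variation between investigators follows from the same formula. With p = 20% in both, an investigator with f = 0 reports 20% and one with f = 50% reports 20% × 0.5 = 10%.

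**Offset from upgrading.** The share of the remaining patients who would have to be raised to Grade ≥3 to cancel the loss is p × f / (1 − p).

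- p = 20%, f = 10%: 0.02 / 0.80 = 2.5%.
- p = 20%, f = 50%: 0.10 / 0.80 = 12.5%.
- p = 10%, f = 10% to 50%: 0.01 / 0.90 = 1.1% to 0.05 / 0.90 = 5.6%.

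Modest upgrading would therefore hide the loss in the total count while leaving individual grades off the cited scale.

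**The case against.** A reader might infer that Grade ≥3 ISR rates in this trial are in fact understated and differ between sites. The documents do not support that. The wording is permissive, and no ulcer frequency, site comparison or regrading rate is given.

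A reader might also infer that the bias can only run downward. That holds for ulcers but not for all ISRs, because the same paragraph could raise other grades.

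Nor would such ulcers be invisible. The verbatim term is meant to name the reaction type, the SAP summarizes by preferred term and by maximum grade, and an ISR listing is planned. An ulcer recorded below Grade 3 could be found there. What the SAP lacks is a rule that connects such terms to the Grade ≥3 outputs.

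The effect on decisions is also limited. The dose search is complete, and safety is reported descriptively. The ISR-specific dose-limiting toxicity item in Protocol 6.4 counts a Grade 3 ISR only if it leads to hospitalization, although the general non-hematologic item there does not exempt ISRs. The ulcers in the monkey study's high-dose group (17.5 mg, against 10.5 mg here) show that the lesion is plausible, but they say nothing about its frequency or grading in patients.

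Finally, clinical judgement in grading is normal. All of this stands as a limit on size and certainty. It does not remove the contradiction, nor the fact that the outputs carry a CTCAE label without saying that the scale may have been modified.

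**Conclusion.** The point holds as a risk to how the grades can be read. Table 11 and the paragraph below it give different answers for a small ulcer. Relative to CTCAE v4.03, Grade ≥3 ISR counts can therefore be understated for ulcers, time to first Grade ≥3 ISR can be delayed or censored for the same patients, and both can vary by investigator.

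The documents fix neither the size nor the net direction across all ISRs. With no regrading there is no effect. On the assumed ranges, up to half of the Table 11 Grade ≥3 patients would be lost from the count, or the loss could be masked by upgrading elsewhere. A firmer statement would need ulcer terms and grades from the trial data.

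**What to change.** 1. **Reconcile the passages.** The sponsor must reconcile Table 11 with the whole paragraph below it, and the CSR must state which grading was applied. The grade also triggers holding and interruption of the vaccine (Protocol 8.3.1 and 8.3.2.2), so no grading or dosing rule is proposed here. Phase 2 has ended and a wording change cannot regrade recorded events, so the CSR statement matters most.
2. **Add to SAP 5.4.1.** Tabulate injection-site ulceration and necrosis terms regardless of assigned grade. Add a sensitivity version of the Grade ≥3 ISR count and of the time-to-first-Grade ≥3 analysis, with those terms set to at least Grade 3 as Table 11 reads. Show it beside the investigator-recorded grade. This version can only equal or exceed the recorded count. It shows the effect of downgrading and does not address upgrading, and it relies on sites having named the ulcer in the verbatim term.
3. **Align the version.** SAP 5.4.1 cites CTCAE 4.0 for adverse events, while the protocol and SAP 5.4.2 cite v4.03. Use v4.03 throughout.

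The cost is one extra derivation on terms that the protocol already asks sites to record, and a possibly less favourable Grade ≥3 ISR rate in the sensitivity table.

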### 8.3.5.2. Management Guidelines for Grade 1 Injection Site Reactions

Irrigation with physiologic saline is recommended. Topical steroids should be applied as appropriate. A mid-strength Class 4 topical steroid is recommended ([National Psoriasis Foundation, 1996-2020](#)). Examples include:

- Flurandrenolide ointment, 0.05%
- Mometasone furoate cream, 0.1%
- Triamcinolone acetonide cream/spray, 0.1%
- Fluocinolone acetonide ointment, 0.03%
- Desoximetasone cream or ointment, 0.05%
- Hydrocortisone valerate ointment, 0.2%

Topical antiseptics or antimicrobials that are likely to cause a skin reaction by initiating an immune response should not be used; however, antibiotics may be used in the presence of infectious findings or positive culture results.

### 8.3.5.3. Management Guidelines for Grade 2/3 Injection Site Reactions

- Irrigation with physiologic saline and use of topical steroids, as described for Grade 1 ISRs above, should be instituted. If topical steroids are not sufficient for ISRs, local (subcutaneous) injection of steroids may be considered
- Topical antibiotics should not be used unless cultures indicate infection
- Open areas may be protected with a non-stick dressing
- Patients with Grade 3 ISRs that do not require hospitalization may remain on study and receive full dose per investigator's judgment
- If an abscess forms, incision and drainage should be carried out to avoid exacerbation of the inflammatory response around the site. After the drainage, the site should be washed with physiologic saline followed by application of topical steroids, as appropriate. Most abscesses should be sterile, but cultures should be obtained (see [Section 8.3.5.2](#) for recommendations for when the culture is positive)

- Emergency measures should be implemented for ISRs > Grade 3

#### **8.4. Packaging and Labeling**

may supply the DSP-7888 bulk product. The study packaging will be performed by a contract manufacturing organization designated by ( Company).

will supply the pembrolizumab (Keytruda - NDC # 0006-3026-02) for Phase 2 of the study. It will be delivered to a contract manufacturing organization designated by INC Research.

All packaging and labeling operations will be performed according to Good Manufacturing Practice (GMP) for Medicinal Products, Regulatory Requirements for Investigational Drug Labeling, and any other relevant regulatory requirements.

#### **8.5. Prior and Concomitant Therapy**

Patients should receive treatment for all inter-current medical conditions or AEs at the discretion of the investigator in conformance with community or institutional medical standards.

All information regarding concomitant treatments (medications or procedures) must be recorded on the patient's case report form/electronic case report form (CRF/eCRF) (including the name of the medication or procedure and duration of treatment).

Palliative and supportive care for disease-related symptoms will be offered to all patients in this study. Patients may receive palliative radiation therapy or palliative surgery for symptomatic lesion(s) as long as the lesion is not the only evaluable one.

Study drug administration should be interrupted during and following these therapies until the patient has adequately recovered from the effects of treatment, as judged by the treating investigator.

Patients on the study will be permitted to receive COVID-19 vaccinations that are authorized for use by the Health Authorities of the country/region.

If possible, a COVID-19 vaccination should be administered on non-study drug injection days. Because DSP-7888 Dosing Emulsion is a peptide vaccine, the COVID-19 vaccine should be administered preferably 48 hours after the DSP-7888 Dosing Emulsion administration to avoid confounding of immediately occurring AEs. The COVID-19 vaccine should also be given at a different injection site from the DSP-7888 Dosing Emulsion injection site.

